4.4 Discontinuation/Early Withdrawal of Participants

4.4.1 Criteria for Discontinuation

Participants could be discontinued from the double-blind period or OLE for any of the following reasons; discontinuation criteria for individual drug arms may also be specified in the drug-specific appendices:

1. Participants would be discontinued from this study if they were involved in any other clinical trial or other research judged not to be scientifically or medically compatible with this study. Participation in any other concurrent clinical trial that studies an investigational drug or any procedures to improve cognition is not permitted.
2. Site principal investigator, Project Arm Leader (PAL), and Medical Director or designee decides participant should be discontinued, e.g., after an SAE or other clinically significant event or laboratory finding. Refer to drug-specific appendices for any drug-specific discontinuation criteria related to adverse events and laboratory findings.
3. Participant or participant research proxy (if participant is cognitively impaired and unable to provide their own consent) decides to withdraw consent, including declining to consent to any protocol amendments.
4. Participant becomes pregnant.
5. Participant non-compliance, based on decision of site study staff or Medical Director. Determination of non-compliance would not apply to doses that are missed or reduced

when the site principal investigator/sub-I, PAL, and Medical Director or designee decide that changes in study drug dosing are necessary for medical or safety reasons. During the CRI period, participants who miss more than two consecutive visits should be evaluated for continued suitability in the trial by the principal investigator/sub-investigator, PAL, and Medical Director or designee.

6. Participant can no longer contribute to the collection of key outcomes data. Thus, a participant who cannot contribute to key endpoints would be discontinued from the double-blind treatment period but eligible for continued clinical and/or cognitive follow-up and/or OLE* (Section 6.3.7).
7. Known negative mutation carrier status or determination that they are no longer at-risk (negative risks status). For example, if a participant enters the study unaware of their mutation status (when allowed), but later learns that they are mutation negative, they would be discontinued from the study.

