In the DIAN-TU-001 study, there was no benefit of gantenerumab observed on the primary endpoint, the DIAN Multivariate Cognitive Endpoint (DIAN-MCE), or on clinical endpoints Clinical Dementia Rating Sum of Boxes (CDR-SB) and Functional Assessment Scale (FAS). However, potential cognitive impact was inconclusive given that the asymptomatic placebo group showed no cognitive decline, and symptomatic patients had declined substantially before reaching target doses. Gantenerumab significantly reduced brain A β deposition, cerebrospinal fluid (CSF) total tau, and CSF pT181, and attenuated the increase of neurofilament light chain

(NfL). A β Pittsburgh compound B positron emission tomography (PiB-PET) results demonstrated significant reduction of A β deposition with gantenerumab compared to placebo at years 2 and 4. Gantenerumab was safe and well tolerated in doses up to 1200 mg SC Q4W (G3). During the placebo-controlled period of the trial, amyloid-related imaging abnormalities-cerebral edema (ARIA-E) were observed in 19.2% (10/48) of the gantenerumab group; compared to the placebo group, participants in the gantenerumab arm were more likely to develop ARIA-E (odds ratio [OR]=9.29, 95% confidence interval [CI]=[1.1, 75.9], p<0.05). ARIA-E cases were PiB+ and 60% had cognitive impairment (CDR>0). ARIA-E cases were mostly asymptomatic for lesion associated neurologic change (8/10); if symptoms occurred (2/10), they were mild in nature and resolved. ARIA-E events were managed by temporarily withholding the dose and resuming at similar or lower doses, with most reaching the target dose (3/10 ARIA-E cases discontinued from the trial, mainly to AD progression). APOE genotype was predictor of ARIA-E. ARIA-E frequency was 31% in APOE- ϵ 4+ and 14% in APOE- ϵ 4- (OR=5.0, 95%; CI [1.0, 30.4], p=0.055). Seventy (70) percent of the ARIA-E cases occurred at higher doses (900 mg or more) and generally after 2 doses of a titration dose. However, the mean severity as measured by Barkhof score was similar regardless of the dose (higher dose=2.8 vs lower doses=3.5).

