16.2.3. PRIMARY ANALYSIS OF KEY SECONDARY EFFICACY VARIABLES

16.2.3.1. Primary Analysis of CDR-SB

The primary analysis will be on the All Gant Exposure mITT, with other baseline covariates (such as baseline EYO) defined in the same way as baseline for the associated population. The recurrent progression is defined as any progression which is either the first increase in CDR-SB above baseline or any progression above the highest preceding post-baseline value identified as a progression, where progression above the preceding value must be observed at two consecutive measurements unless the progression occurs at the last measurement. Subjects without a progression event at their last measurement will be censored at the time of that measurement. The time-to-event is the time elapse between the two visits where the recurrent progression is observed, or the time since the baseline assessment for the first progression. Subjects can contribute multiple records to the analysis (i.e., once for each progression and potentially for censoring at the time of last measurement). The same definition will be applied to all controls as defined in [Section 5.4](#). The Cox proportional hazards model employing the Andersen-Gill method (Prentice RL, 1981) with robust variance estimator will be used to compare the hazards of recurrent progression in CDR-SB between population and all controls. The model will include treatment group and baseline EYO as the fixed effects. Should the model produce a two-sided p-value less than 0.10, a sensitivity analysis will be conducted using the shared frailty method (add reference).

Author: [REDACTED]

Version Number:

7

Version Date:

07Dec2023

Template No.: CS_TP_BS016 Revision 6

Reference: CS_WI_BS005

Effective Date: 02Dec2019

Analyses will be conducted separately for baseline asymptomatic and symptomatic subjects.

The same analysis will be applied to the OLE Gant mITT population and the OLE Gant All Gant exposure mITT populations, along with all controls. The analysis will also be conducted for each of the three mITT populations based on the baseline asymptomatic and symptomatic subjects presented separately. A Kaplan-Meier figure will be generated for baseline asymptomatic subjects for all three mITT populations and associated controls.

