16.2.4. SUPPLEMENTAL ANALYSIS OF KEY SECONDARY EFFICACY VARIABLES

16.2.4.1. Supplemental Analysis of CDR-SB

16.2.4.1.1. Subgroup Analysis for CDR SB

Each subject in the All Gant exposure mITT population and all controls will be categorized into 3 groups by comparing the baseline and the last available PiB SUVR values to 1.25: (1) Amyloid normal group (both the baseline and the last available PiB SUVR values <1.25); (2) Amyloid abnormal to normal group (the baseline PiB SUVR value ≥ 1.25 and the last available PiB SUVR value <1.25); (3) The rest (not in groups (1) and (2)). The model described in [Section 16.2.3.1](#) will be applied to the All Gant exposure mITT population and all controls to compare the hazard of progression in CDR SB among these 6 subgroups (i.e., 3 groups above assessed within baseline asymptomatic/symptomatic status).

A separate analysis will identify DIAN-TU-001 subjects as either PiB-PET SUVR normal or abnormal based upon the last post-baseline measurement for the subject. The model described in

Author: [REDACTED]

Version Number:

7

Version Date:

07Dec2023

Template No.: CS_TP_BS016 Revision 6

Reference: CS_WI_BS005

Effective Date: 02Dec2019

Section 16.2.3.1 will be applied to the asymptomatic subjects in the All Gant exposure mITT population where treatment groups are replaced with the three groups of PiB-PET SUVR normal, PiB-PET SUVR abnormal, and external controls, with the normal and abnormal groups being compared to the external controls and to each other. The model will also be run with factors of the number of post-baseline PiB-PET normal values (as a continuous measure to replace the normal/abnormal status) and the interaction of that variable with the treatment groups.

The model described in **Section 16.2.3.1** will be applied to the asymptomatic subjects in the All Gant exposure mITT population where treatment groups are replaced with the three groups of gantenerumab exposure, concurrent controls, and non-concurrent controls, with the gantenerumab exposure being compared to both sets of controls.

Figures of model estimated mean over time by treatment arms or spaghetti plots of individual data over time/EYO by treatment arms will be presented as deemed necessary by Washington University team and may be included in CSR as needed. The plots will also be presented separately for baseline asymptomatic and symptomatic subjects at the OLE baseline.

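### Amyloid groups fixed by the last PiB scan or by the number of normal scans can appear linked to slower CDR progression with no effect, if progression cuts later scanning or baseline amyloid confounds

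*SAP*

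**What the plan says.** SAP 16.2.4.1.1 sets three amyloid groupings.

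- **Three groups within symptom status (first paragraph).** These use the baseline and last available scans. The converted group, for example, has "the baseline PiB SUVR value ≥ 1.25 and the last available PiB SUVR value <1.25".
- **Two levels (second paragraph, baseline-asymptomatic participants).** Participants are classed "as either PiB-PET SUVR normal or abnormal based upon the last post-baseline measurement for the subject", and the SAP describes a model "where treatment groups are replaced with the three groups of PiB-PET SUVR normal, PiB-PET SUVR abnormal, and external controls".
- **Count (same paragraph).** The model is rerun with the "number of post-baseline PiB-PET normal values (as a continuous measure to replace the normal/abnormal status").

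All three use the Cox model of SAP 16.2.3.1. There, time to first progression runs from the baseline assessment, and "The model will include treatment group and baseline EYO as the fixed effects". No time-dependent term, landmark or baseline PiB covariate is named for these Cox models. SAP 16.4 adds baseline PiB, but for the annual-rate analyses.

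The groupings return in 16.2.4.1.2 (first CDR-SB progression) and 16.2.4.2 (CDR Global). In Table B the post-baseline PiB groupings are sensitivity analyses of both primary interim endpoints. The stated objective there is whether amyloid level is associated with lower progression risk, which the table glosses as delay of progression.

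**The concern.** The clock starts at baseline, but the label is settled by scans made up to years later. A participant who progresses and stops being scanned has fewer chances of a normal scan, so may be labelled abnormal because of the progression. The documents make such a link plausible:

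- Protocol 4.4.1 lists as a reason for discontinuation: "Participant can no longer contribute to the collection of key outcomes data".
- Appendix 3, 1.4 reports of the double-blind period: "3/10 ARIA-E cases discontinued from the trial, mainly to AD progression".
- OLE entry requires that the participant can receive drug and safety assessments (Appendix 3, 3.2.1).
- Normal scans are likely to come late. Appendix 3, 1.6 says the double-blind regimen did not fully remove plaque, and OLE titration alone takes 15 months (1.5.2.1).

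Confounding is a second route. The two-level normal group includes people who were never abnormal. Protocol 3.1 reports very low amyloid in close to 30% of participants at EYO -15 to -10. If such people also progress more slowly, normal scans will track slow progression whatever the drug does.

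At stake is how the CSR reads the relation between clearing amyloid and delaying CDR progression.

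**Working it through.** **Plan figure.** The documents give no event count, power or hazard ratio for these models, so there is nothing to reproduce. The one usable rate is the 5% annual dropout in Appendix 3, 4.1.2. It does reproduce the stated 51 to 77 completers: 60 × 0.95³ = 51.4 and 90 × 0.95³ = 77.2.

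**Mechanism.** The model as written is h(t) = h0(t)·exp(b·G + c·EYO), with G fixed by the last scan. Assume a median of 4 years to a normal scan, unrelated to progression. A participant scanned for 7 years is labelled normal with probability 1 − 2^(−7/4) = 0.70. One who progresses and leaves at 3 years has probability 1 − 2^(−3/4) = 0.41. The gap comes from follow-up alone.

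**Null simulation (amyloid change has no effect on progression).** From the documents: 5% annual dropout before progression. Assumed: annual scans; progression rate 0.10 or 0.20 per year; median 2.5 to 4 years to a normal scan; mixed follow-up (60% for 3 years, 40% for 7 to 10 years) or 3 years for all; dropout after progression 1, 2, 3 or 5 times the earlier rate. Multiples of 3 and 5 mean 15% and 25% a year. EYO was not simulated, because the hazard was otherwise equal across participants.

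Hazard ratios (AG = Andersen-Gill):

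| Follow-up, progression rate | Dropout multiple | Last scan, AG | Last scan, first event | Per normal scan, AG | Time-dependent, AG |
|---|---|---|---|---|---|
| Mixed, 0.10 | 1 | 1.01 | 1.00 | 1.00 | 1.05 |
| Mixed, 0.10 | 2 | 0.90 | 0.86 | 0.97 | 1.03 |
| Mixed, 0.10 | 3 | 0.77 | 0.73 | 0.93 | 0.93 |
| Mixed, 0.10 | 5 | 0.62 | 0.58 | 0.89 | 1.00 |
| Mixed, 0.20 | 3 | 0.83 | 0.77 | 0.95 | 0.96 |
| Mixed, 0.20 | 5 | 0.74 | 0.65 | 0.92 | 1.06 |
| 3 years, 0.20 | 1 | 1.01 | 1.02 | 0.99 | 0.94 |
| 3 years, 0.20 | 3 | 0.91 | 0.89 | 0.96 | 1.03 |
| 3 years, 0.20 | 5 | 0.76 | 0.70 | 0.87 | 0.97 |

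Reading the SAP's elapsed time between visits as gap time gave a similar bias (0.66 to 0.86 at multiples of 3 to 5).

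**Against controls with the same hazard** (multiples 3 to 5, AG): normal 0.83 to 0.96, abnormal 1.11 to 1.22, all gantenerumab 0.96 to 1.02. The split makes one group look better and the other worse when the whole shows nothing.

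**Baseline confounding alone** (multiple 1; 15% to 30% normal at baseline with 0.25 to 0.5 times the hazard): last-scan AG hazard ratio 0.70 to 0.87. Time-dependent coding without baseline adjustment gave 0.53 to 0.77, so it does not cure this.

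**Both problems together, testing the remedy** (first event; baseline amyloid affects both hazard and ease of normalising):

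| Model | ×1 | ×2 | ×3 | ×5 |
|---|---|---|---|---|
| As written | 0.65 | 0.60 | 0.57 | 0.53 |
| Baseline PiB added only | 1.02 | 0.93 | 0.87 | 0.79 |
| Time-dependent only | 0.62 | 0.62 | 0.62 | 0.62 |
| Both | 1.04 | 1.04 | 1.04 | 1.04 |

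A further null simulation agreed. The last-scan hazard ratio was 0.76 to 0.92 at multiples of 3 to 5, and 0.46 to 0.58 with baseline confounding. With both corrections it was 0.95 to 1.05.

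**False findings.** With 40 to 60 participants and no baseline confounding, the rate of p<0.05 in favour of normal (nominal 2.5%) was 2–3%, 9–12% and 14–19% for the last scan at multiples 1, 3 and 5. For the count it was 4–5%, 12–16% and 20–27%. Part of the count excess is a liberal robust test, which rejected 9–10% two-sided at multiple 1.

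**The case against.** The strongest reply is that a label fixed after baseline need not bias anything here. The last scan may fall before or after the event, and the simulations give about 1 when scanning is unrelated to progression and baseline amyloid is unrelated to hazard. That stands, and it makes the concern conditional.

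The evidence for the condition is also indirect:

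- A reader might infer that decline itself is a discontinuation criterion. Protocol 4.4.1 says inability to contribute key outcomes, and leaves those participants eligible for follow-up and/or the OLE.
- Protocol 6.3.7 and Appendix 3, 3.2.8 encourage biomarker visits after dosing stops.
- The ARIA-E discontinuations are three cases, while the two-level and count models use only baseline-asymptomatic participants. Nothing shows that such participants stop scanning after a first CDR rise.

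The size depends on follow-up. With progression 8% and normalisation 15% a year, and 10%, 20% or 30% of progressors stopping scans each year, 3-year follow-up gave 0.90, 0.88 and 0.84. Nine-year follow-up gave 0.76, 0.63 and 0.57. Participants first exposed in the OLE have at most about 3 years planned.

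A reader might also infer that every version ignores baseline amyloid. The three-group version already splits at 1.25, so that criticism applies to the two-level and count models.

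What remains is that nothing in the SAP guards against either condition, and both are plausible in this trial.

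**Conclusion.** The concern holds in conditional form. If progression reduces later scanning or OLE entry, or if baseline amyloid drives both progression and ease of normalising, these models can link normal amyloid with slower progression with no effect. Under the null, normal versus abnormal is roughly 0.6 to 0.9 at 3 to 5 times higher dropout after progression. It is nearer 1 with 3-year follow-up or against controls, and lower with baseline confounding added. These values rest on assumed progression, normalisation and dropout rates; they are not predictions for this trial.

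Two stronger readings are not supported. One is that the trial's main results are compromised. The primary PiB MMRM and the main treatment-versus-control Cox models do not use these labels, and the affected analyses are supplemental or sensitivity. The other is that the interim decision was distorted. The SAP version history says the interim led to early termination of the OLE; it does not say these analyses drove that decision. The practical consequence now lies in the final CSR.

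**What to change.** In SAP 16.2.4.1.1, and where it is reused for CDR-SB (16.2.4.1.2) and CDR Global (16.2.4.2):

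1. Make amyloid status time-dependent. It starts from the baseline scan, so baseline-normal participants start as normal, and it is updated at each later scan date. Update the count of normal scans in the same way.
2. Add continuous baseline PiB SUVR to the two-level and count models. The model becomes h(t) = h0(t)·exp(b·N(t) + c·EYO + d·baseline PiB), where N(t) is status, or count, at the latest scan up to time t. External controls stay a separate group.
3. Keep the last-scan version as descriptive only, with a sentence on why it may mislead.
4. State that status is carried forward where no PiB scan was done, for example in the common-close years, when biomarkers were not assessed (Appendix 3, 1.9.2).

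Both of the first two steps are needed.

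The cost is a SAP paragraph and start-stop records built from scans already collected. Status will be stale between scans. Participants and controls without a baseline PiB scan drop out of the adjusted models, so their number should be reported; the SAP version history notes missing baseline PET. With 40 to 60 participants, the robust test on time-dependent status was itself liberal (8–10% two-sided at multiple 1), so the CSR should rest on estimates and intervals rather than p-values.

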This is an adaptive platform-based study, with flexibility to add new investigational products to the protocol, allowing participants to be randomized to study drug arms open to enrollment, and for the study to maintain a cohort of trial ready participants with or at risk for DIAD mutations. Data from the platform's placebo drug arms will continue to be utilized by subsequent drug arms as control data, in addition to the DIAN-OBS matched control data.

Figure 3 DIAN-TU-001 Master Protocol AD Prevention Platform Design

The first two drug arms tested in the platform were the gantenerumab and solanezumab study drug arms, with each enrolled participant randomized to active drug or the corresponding placebo (“direct placebo”). The double-blind periods concluded for both drug arms with an open-label extension (OLE) of gantenerumab opened to any of the participants enrolled in either of the double-blind drug arms. Changes, such as to the enrollment criteria (e.g., the EYO range for inclusion), may be made based on the specific therapeutic compounds being tested and the stage of disease that is most likely to be targeted by a therapy. Results from the completed solanezumab and gantenerumab arms in DIAN-TU-001, which included an EYO range of -15 to +10, found that close to 30% of participants at an EYO range of -15 to -10 had very low amyloid PET levels, and thus had minimal to no detectable tau pathology. Therefore, the change to the EYO entry criteria for CRI and future tau-based therapeutics to -10 to +10 in Amendment 11 will increase the likelihood of participants having some tau-related changes that can be measured during the double-blind period of the trial. The third drug arm added to the platform was the atabecestat arm which was prematurely discontinued due to safety (Novak, G, et al. 2020). For further information relevant to the completed testing periods of these study drug arms, see earlier version(s) of the protocol.

Additional study drug arms will continue to follow the same core procedures for measuring biomarker, cognitive, and clinical measurements, thereby allowing continued sharing/pooling of placebo data across study drug arms.

Starting with Amendment 8, a CRI period was opened for recruitment and enabled for future drug arms. With Amendment 9, the CRI period was expanded to include 2 participant

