16.1.4.4. Proportion of Subjects Converted from Abnormal to Normal

To evaluate whether gantenerumab can decrease the accumulated amyloid plaque from abnormal level to normal level, the threshold of 1.25 will be used to define normal level vs abnormal level at the OLE baseline and at each post-baseline visit. A PiB-PET SUVR >1.25 is considered abnormal while a PiB-PET SUVR ≤ 1.25 is considered normal. A shift from OLE baseline to

Author: [REDACTED]

Version Number:

7

Version Date:

07Dec2023

Template No.: CS TP BS016 Revision 6

Reference: CS WI BS005

Effective Date: 02Dec2019

each post-baseline visit, where missing values are replaced using last observation carried forward (allowing the baseline value to also be carried forward), and to the last post-baseline OLE measurement will be provided along with a corresponding Fisher's exact test. A supportive analysis of shifts at each post-baseline visit without carrying forward values will also be provided. This analysis will be conducted for the OLE Gant mITT population.

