17. SUBSET OF ANALYSES AT THE INTERIM

The two objectives of the interim analysis are to determine if gantenerumab OLE treatment results in clinical benefit and determine the extent of amyloid removal compared to the double-blind period. The primary analyses for the interim will be the primary analysis of CDR Global

Author: [REDACTED]

Version Number:

7

Version Date:

07Dec2023

Template No.: CS TP BS016 Revision 6

Reference: CS WI BS005

Effective Date: 02Dec2019

(in Section 16.2.3.2) and CDR-SB (in Section 16.2.3.1) applied to subjects who are asymptomatic at baseline for the All Gant Exposure mITT and main set controls.

The following subset of analyses will be conducted separately for baseline asymptomatic and baseline symptomatic subjects, except where noted for select imaging and fluid biomarker analyses, at the interim analysis and additional exploratory analyses will be conducted as needed, noting that focus will be on Year 2 findings in the absence of Year 3 findings, with any imputation for Year 3 excluded. These analyses will be conducted for the each of the three mITT populations and controls as specified for each model, unless the associated section describes the analysis as being conducted on select mITT populations, noting that when multiple models are described within a section, only the first one will be conducted for the interim unless otherwise specified. By-visit descriptive statistics during OLE will be displayed, overall and by OLE baseline symptomatic status, for each associated parameter, including each component of the OLE cognitive composite.

[REDACTED] [REDACTED]

Author: [REDACTED]

Version Number: 7

Version Date: 07Dec2023

Template No.: CS_TP_BS016 Revision 6

Reference: CS_WI_BS005

Effective Date: 02Dec2019

Table B: Interim Analysis Models

Endpoint	Analysis Tier and Statistical Method	Objective
CDR Global	Primary: 16.2.3.2: Cox proportional hazards time to first progression	To evaluate whether the treatment delays the disease progression
	Sensitivity: 16.2.4.2 (third paragraph): post-baseline PiB-PET SUVR normal	To evaluate whether normal / abnormal amyloid levels are associated with lower risk of first progression (delay of disease progression) in CDR Global compared to all controls
	Sensitivity: 16.2.4.1.1 (third paragraph): comparison to concurrent and non-concurrent controls	To evaluate whether the treatment delays the disease progression in CDR Global compared to the concurrent and non-concurrent controls

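### The last-scan PiB-PET grouping pools never-abnormal participants with those cleared on treatment, so a lower hazard in the normal group cannot be credited to amyloid clearance

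*SAP*

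**What the plan says.** - **Label.** SAP 16.2.4.1.1, second paragraph, classes each trial participant as PiB-PET normal or "abnormal based upon the last post-baseline measurement for the subject".
- **Comparison.** In asymptomatic members of the All Gant exposure mITT, the treatment groups are replaced by "PiB-PET SUVR normal, PiB-PET SUVR abnormal, and external controls, with the normal and abnormal groups being compared to the external controls and to each other".
- **Second version.** The model is run again with "the number of post-baseline PiB-PET normal values (as a continuous measure to replace the normal/abnormal status").
- **Adjustment.** The model is taken from 16.2.3.1: "The model will include treatment group and baseline EYO as the fixed effects". The CDR Global model in 16.2.3.2 has the same two terms.
- **CDR Global.** SAP 16.2.4.2, third paragraph, applies the same grouping. It mentions categorising external controls too, but the scheme that it points to keeps them as one group.
- **Interim.** SAP 17, Table B, lists this grouping as a sensitivity analysis for CDR Global ("post-baseline PiB-PET SUVR normal") and lists both versions for CDR-SB.
- **The alternative in the same section.** The first paragraph of 16.2.4.1.1 does use baseline. It sets up an "Amyloid normal group (both the baseline and the last available PiB SUVR values <1.25"), a separate abnormal-to-normal group, and a remainder. Table B does not list this split.
- **Population.** Under SAP 5.3 the clinical analyses use the mITT set defined on CDR Global, which has no amyloid requirement.

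**The concern.** A participant whose SUVR is below 1.25 at every scan falls in the normal group without any change in amyloid, and also has a high count of normal scans. Such participants are foreseen: SAP 7.1 lists baseline SUVR of 1.25 or less as a category. Protocol 3.1 reports that in the completed arms "close to 30% of participants at an EYO range of -15 to -10 had very low amyloid PET levels". Protocol 1.3 says that nondemented people with amyloid are more likely to decline, so pooling never-abnormal participants with cleared ones favours the normal group.

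The interim asks whether treatment brings clinical benefit, and these analyses use the population of the interim primary analyses. A reader who sees a low hazard ratio in the normal group will naturally take it as a sign that removing plaque delays progression. This grouping cannot tell clearance from an amyloid-free start. The fault is one of baseline composition, and it would remain even if the last scan were known on day one.

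**Working it through.** The SAP gives no sample size, event count or power for this analysis, so there is no plan figure to reproduce. The never-abnormal share and its hazard are not in the documents either. All sizes below are assumptions.

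**Step 1: closed form, no clinical drug effect.** Let *a* be the share of treated participants never abnormal, *c* the share moved from abnormal to normal, and *r* the hazard of never-abnormal relative to baseline-abnormal participants.

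- Normal against abnormal: HR = (a·r + c)/(a + c).
- Normal against controls with the same never-abnormal share: divide that by (a·r + 1 − a).

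With a = 0.2 and c = 0.2:

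| r | normal vs abnormal | normal vs controls |
|---|---|---|
| 1 | 1.00 | 1.00 |
| 0.7 | (0.14 + 0.2)/0.4 = 0.85 | 0.85/0.94 = 0.90 |
| 0.5 | (0.10 + 0.2)/0.4 = 0.75 | 0.75/0.90 = 0.83 |
| 0.3 | (0.06 + 0.2)/0.4 = 0.65 | 0.65/0.86 = 0.76 |

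Over a = 0.1 to 0.3, c = 0.1 to 0.4 and r = 0.3 to 0.7, the first ratio runs from (0.09 + 0.1)/0.4 = 0.475 to (0.07 + 0.4)/0.5 = 0.94. The second runs from 0.60 to 0.97.

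**Step 2: simulation with EYO in the model.** Assumptions:

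- 60 treated participants and 75 controls, 1,000 replicates.
- EYO uniform from −15 to 3; chance of never being abnormal falls with EYO and averages 25%.
- Hazard rises with EYO; follow-up is 2 to 7 years.
- 35% of baseline-abnormal treated participants convert, at random, with no effect on progression.
- Cox model for the first event with group and EYO.

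| r | HR as planned, normal vs abnormal | p < 0.05 in protective direction | HR, converted vs still abnormal, never-abnormal separated | p < 0.05 in protective direction |
|---|---|---|---|---|
| 1 | 0.99 | 2.5% | 1.00 | 1.5% |
| 0.7 | 0.90 | 5.3% | 0.96 | 1.9% |
| 0.5 | 0.86 | 6.6% | 0.99 | 2.4% |
| 0.3 | 0.79 | 7.3% | 1.00 | 1.8% |

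The nominal protective-direction rate is 2.5%, half of the two-sided 5% in SAP 6.5. The simulation error on 7.3% is √(0.073 × 0.927/1000) = 0.8 points.

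**Step 3: why EYO does not absorb the bias.** In SAP Appendix 3, EYO rests first on mean onset age by mutation. Taking the listed SE as SD/√n, APP Val717Ile gives 0.7 × √136 = 8.2 years, PSEN1 Ala431Glu 0.4 × √97 = 3.9 and PSEN1 Gly206Ala 1.1 × √75 = 9.5. With that spread, EYO is a noisy marker of stage, and baseline amyloid adds information that the model leaves out.

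**The case against.** The case for leaving the plan alone has several sound parts.

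- **Tier.** Table B calls this a sensitivity analysis and asks about association. The interim primary analyses do not use the label, and no decision rule hangs on it. This stands.
- **Timing.** The interim data cut was 31 March 2023. The summary of changes in SAP version 7 (7 December 2023) records that the interim led to early termination of the extension. New wording cannot alter that interim. It can still affect how its results are read and what the final report shows.
- **The split exists.** The first-paragraph grouping is planned for the final analysis in 16.2.4.1.1 to 16.2.4.1.5, 16.2.4.2 (second paragraph) and 16.4. This narrows the gap to the second-paragraph analyses and to Table B.
- **A built-in check.** Both groups are compared with controls. With a = 0.25, r = 0.5 and no clearance, the control hazard is 0.125 + 0.75 = 0.875, so the normal group shows 0.5/0.875 = 0.57 and the abnormal group 1/0.875 = 1.14. A careful reader would see both. But a ratio near 1.14 is hard to tell from 1 in groups this small, and can itself be misread as harm from residual amyloid.
- **Low-amyloid share.** The figure near 30% covers only EYO −15 to −10, and very low is not defined as SUVR below 1.25. The 25% used above may be too high.

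Three stronger readings are tempting and not supported. First, a reader might infer that the SAP counts always-normal participants as normalised. It calls them normal and claims only association. Second, setting c = 0 makes the normal-against-abnormal ratio equal r, which suggests a far larger bias. Protocol Appendix 3, section 1.4, reports significant amyloid reduction on gantenerumab, so zero clearance is not a fair base case. Third, a reader might infer that the interim conclusion was undermined. Nothing in the documents ties it to this analysis.

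**Conclusion.** The concern holds in limited form. As written, the second-paragraph grouping and the count of normal scans mix participants who began without abnormal amyloid with those cleared on treatment. A lower hazard in the normal group is therefore not evidence about clearance. The bias vanishes only if never-abnormal carriers progress like others of equal EYO.

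Its size rests on assumptions: about 0.79 to 0.90 for the EYO-adjusted ratio with 25% never abnormal and a relative hazard of 0.3 to 0.7. The main harm is a biased hazard ratio, since false positives rise only to about 5% to 7%. The simulation covers first progression, not the recurrent-event model for CDR-SB. Its return to about 1 after separation assumes that conversion is unrelated to prognosis.

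**What to change.** 1. In SAP 16.2.4.1.1 (second paragraph) and 16.2.4.2 (third paragraph), restrict the normal/abnormal comparison and the normal-scan count to participants with baseline PiB SUVR ≥ 1.25. Compare them with external controls who are also ≥ 1.25 at baseline.
2. Show always-normal participants as a separate row, against external controls below 1.25 at baseline.
3. List the first-paragraph split beside these analyses in Table B. If the interim is already complete, report the split beside them when interpreting the interim results and in the final study report.
4. Keep the present unsplit result as a descriptive supplement.
5. While editing, settle two small inconsistencies. SAP 16.1.4.4 says "A PiB-PET SUVR >1.25 is considered abnormal while a PiB-PET SUVR ≤ 1.25 is considered normal", whereas the first paragraph of 16.2.4.1.1 puts a value of exactly 1.25 on the abnormal side. Table B also states the objective against all controls where 16.2.4.1.1 names external controls.

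The work is SAP wording and a grouping variable that largely exists already. The real cost is smaller groups: participants and controls without a baseline PiB scan drop out, and the summary of changes in SAP version 7 reports substantial missing PET data. The restriction also leaves a comparison that depends on a post-baseline scan, so the wording should stay associational.
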